2.4.3 Study Day, Analysis Visit Windows and Baseline

Subject visits will be analyzed by nominal visit and/or time point as recorded on the CRFs, given that the day on which the visit occurs falls into the appropriate window as described in the table below. If a visit date does not fall into the correct window, data from that visit will not be summarized in the tables, but it will be included in the listings.

Study Day will be calculated from the reference date, and will be used to show the start and stop day of assessments and events.

The reference date is defined as the day that the first injection is administered, that is, Day 0.

Study Day = (date of event – date of Day 0).

The analysis will utilize less stringent visit windows than defined in the protocol, as defined below. If a subject has more than one visit in a visit window, the visit closest to the scheduled day will be considered for the analyses. If the difference is a tie, the day before the scheduled day will be used in the statistical analyses.

Unless otherwise specified, baseline is defined as the last non-missing measurement taken prior to reference start date (excluding unscheduled assessments). In the case where the last non-missing measurement and the reference start date coincide, that measurement will be considered pre-baseline, but Adverse Events (AEs) and medications commencing on the reference start date will be considered post-baseline.

Unscheduled visit measurements will not be used to provide a measurement for either baseline values or post-treatment values. Unscheduled data will be included in the standard subject listings but not in the summary tables.

Table 2 Visit Window

Analysis Visit	Scheduled Day	Start of Window (Study day)	End of Window (Study day)
Screening	-30	-30	<0
Day 0	0	0	0
Month 3	90	80	100
Month 6	182	167	197
Month 9	273	258	288
Month 12	365	335	395
Month 15	455	420	490
Month 18	548	503	593
LTFU 1 (Month 24)	730	685	775
LTFU 2 (Month 30)	912	867	957
LTFU 3 (Month 36)	1095	1050	1140

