
(6) Photos of largest ulcer on the index leg as well as a photo or photos (if necessary) of the entire index leg to show all ulcer/gangrene locations. Debridement should be performed prior to these evaluations;

(7) Procedure must be performed prior to a planned interventional treatment (revascularization or amputation) while on study.

** For the purposes of this study a month is defined as 30 days. Days 14, 28 and 42 are calculated from either Day 0, Month 3, Month 9 or Month 12. All (non-dosing) follow-up visits should be calculated based on Day 0/Baseline.

Table 4: Schedule of Sample Collection for the Serum HGF Protein & PCR for HGF Plasmid Assays

Schedule of Sample Collection for the Serum HGF protein & PCR for HGF Plasmid Assays																	
PROCEDURE	Dosing Visit: First Cycle	PK Sampling Visit	Dosing Visits: First Cycle							Follow Up Visit	Dosing Visits: Second Cycle				PK Sampling Visit	Dosing Visit: Second Cycle	Follow Up Visit
Time	Day 0	Day 4	Day 14	Day 28	Day 42	Month 3	Month 3 Visit + 14 Days	Month 3 Visit + 28 Days	Month 3 Visit + 42 Days	Month 6	Month 9	Month 9 Visit + 42 Days	Month 12	Month 12 Visit + 4 days	Month 12 Visit + 42 Days	Month 15	
Vist Window	Baseline	0	± 2 days	± 2 days	± 3 days	± 7 days	± 2 days	± 2 days	± 2 days	± 7 days	± 7 days	± 2 days	± 7 days	0	± 2 days	± 7 days	
Serum HGF protein Assay	X*	X	X*	X*	X*	X*			X*		X*		X*	X			X
PCR for HGF plasmid DNA Assay	X*	X	X*	X*	X*	X*	X*	X*	X*	X	X*	X*	X*	X	X*	X*	X

*At Dosing Visits (indicated by the shaded columns), two (2) samples should be drawn one pre-dose and a second drawn four hours post-dosing.

** The first 5 subjects who were randomized and received test medication will have blood samples drawn for PK 4 days following their Month 9 Visit.

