5.2. Confirmation of Subjects' CLI Stability Pre-Dose

Sites must perform an assessment of the subject's CLI status in order to confirm stability prior to dosing. The stability assessment should occur on Day 0 prior to dosing (≥ 2 weeks between the screening and the Day 0 assessments), and should include ulcer and leg photography and tracings of the largest ulcer on the index leg (with ulcer debridement, if necessary, occurring prior to photography and tracing), hemodynamic measurements, and measurement of ischemic rest pain

severity. The assessment will confirm that the ulcer(s) and gangrene have not increased in size excessively so that the subject requires a surgical intervention or decreased in size excessively so that the subject's lesions will heal spontaneously without study product. The assessment will also confirm that hemodynamic measurements have not changed markedly ($\pm > 0.1$ ABI or TBI) and the ischemic rest pain has not increased or decreased greatly despite continuing the same dose of analgesics. Subjects with unstable CLI will not be randomized. They will be considered screen failures. The entry committee will verify the CLI stability post-randomization

5.3. Dosing Visit Study Procedures: Day 0

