5.3.1. Pre-Dosing Procedures

1. Medical History Review
2. Physical Exam
3. Peripheral Vascular Intervention Update
4. Assessment of CLI status (associated measurements are listed separately)
5. Ulcer tracings as described in Section 5.2 Confirmation of Subjects' CLI Stability Pre-Dose
6. Ulcer photographs as described in Section 5.2
7. Hemodynamic measurements (ankle and toe pressures and estimation of ABI and TBI)
8. QOL Measurements (VascuQol Questionnaire)
9. Ischemic Rest Pain severity measured using the VAS pain scale (see Appendix E)
10. Collect Laboratory Test samples for the following: Hematology, Chemistry, CBC, Urinalysis, Urine Pregnancy test, if applicable (see Appendix G), and anti-HGF antibody sample
11. Collect Pre-dose samples for the Serum HGF protein assay and the PCR for HGF Plasmid DNA assay
12. Concomitant Medication review

5.3.2. Dosing Procedures: Day 0

After successful completion of the pre-dose procedures and confirmation that the subject's CLI status is stable, the subject may receive the first dose of study product. Study product should be administered to the subject by 8 IM injections in the index leg utilizing the appropriate 21G needle and syringe as described in the Study Drug Administration Instructions. The 8 injection site locations will have been determined based on the location of the diseased vessels. Additionally, duplex scanning must be used during the injection procedure to further clarify the injection site locations (See Appendix A).

The injection sites will be marked with a tattoo or similar pen prior to injecting the study product on Day 0. The procedure will be repeated on injections made on Day 14, Day 28, and Day 42 using a different color tattoo or similar pen to track the injections. The Day 14, Day 28, and Day 42 injection sites will be 1-2 cm initially proximal to the Day 0 injection then 1-2 cm distal and

subsequently 1-2 cm lateral, respectively. No more than 3 injections should be made into the anterior or lateral compartments on any dosing visit.

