9. EVALUATIONS AND STATISTICAL METHODS

9.1. Evaluations

The following evaluations relating to tolerability, safety and clinical benefit will be made:

1. Adverse events (AEs) suspected to be related to injections of HGF plasmid
2. Discontinuations related to adverse effects from the injections of HGF plasmid
3. All AEs up to Month 3, Month 6, Month 12, and Month 18
4. Serious adverse events (SAEs) up to Month 3, Month 6, Month 12, and Month 18
5. Number of deaths and cause over the 18 month period up to Month 3, Month 6, Month 12, and Month 18
6. Number of subjects in whom the largest ulcer healed completely or gets smaller (photo confirmation) at 6, 12 and 18 months (cumulative)
7. Number of subjects in whom rest pain (based on the 100 mm VAS scale) reduces by 20 mm or more or was completely relieved at 6, 12 and 18 months (cumulative)
8. Change in VascuQol Questionnaire (QOL) score compared to the baseline at 6, 12 and 18 months
9. Number of subjects revascularized (bypass or endovascular intervention) up to Month 3, Month 6, Month 12, and Month 18
10. Number of subjects with minor and number of subjects with major amputations (at or above the ankle) up to Month 3, Month 6, Month 12, and Month 18

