APPENDIX B. HEMODYNAMIC PROCEDURES

ABI and TBI Assessment

Explain the procedure, reassure the subject, and ensure that he/she is lying flat and is comfortable, relaxed, and rested with no pressure on the proximal lower limb vessels. Laying the subject supine reduces the hydrostatic pressure inaccuracies. Reliability and ability to reproduce results both over time and between observers was tested and the index was found to vary by 0.06, which is considered acceptable. Measuring the pressure in both arms and using the higher of the two pressures increases the non-invasive accuracy of measurement of central systolic pressure but will not eliminate this potential limitation to the method.

Measure the brachial systolic blood pressure:

1. Place an appropriately sized cuff around the upper arm
2. Locate the brachial pulse and apply ultrasound contact gel
3. Angle the Doppler probe at 45 degrees and move the probe to obtain the best signal
4. Inflate the cuff until the signal is abolished then deflate the cuff slowly and record the pressure at which the signal returns being careful not to move the probe from the line of the artery
5. Repeat the procedure for the other arm
6. Use the highest of the two values to calculate the ABI

Measure the ankle systolic pressure:

1. Place an appropriately sized cuff around the ankle immediately above the malleoli having first protected any ulcer that may be present
2. Examine the foot, locating the dorsalis pedis pulse and apply contact
3. Continue as for the brachial pressure, recording this pressure in the same way
4. Repeat this for the posterior tibial artery
5. Use the highest reading obtained to calculate the ABI for that leg

Measure the toe systolic pressure:

1. Place an appropriately sized cuff around the hallux (1st toe) having first protected any ulcer that may be present. If the 1st toe is unavailable you may use other toes if appropriate, this should be documented in the source documents.
2. Examine the toe with the Doppler or PPG (photoplethysmograph), locating the pulse on the dorsal aspect and apply contact.

Note: The same method (Doppler or PPG) must be used on the subject for all assessments through study completion.

3. Continue as for the ankle pressure, recording this pressure in the same way
4. Repeat this for the plantar toe artery
5. Use the highest reading obtained to calculate the TBI for that leg

Problems and errors may arise if:

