A summary table including counts and percentages and a listing will be provided for these parameters for the following time periods: up to Month 6, 0 to Month 12, and 0 to Month 18.

As a supplemental analysis, time to major amputation or death will be performed, and the Kaplan-Meier (KM) estimates with 2-sided 95% confidence interval using Greenwood's formula will be computed up to the end of the study and plotted. If a subject undergoes major amputation followed by death, it will be counted as an event. If a subject does not experience major amputation or death, the subject will be censored at the date of last contact as recorded on the CRFs.

- **Shift from baseline in Rutherford classification**

Shift from baseline in Rutherford classification will be summarized by study visit.

- **Quality of life (QoL)**

Quality of life (QoL) measurements will be assessed using the disease-specific vascular Quality-of-Life questionnaire (VascuQol). The VascuQol contains 5 domains (pain, symptom, activities, social, and emotional functioning), and responses are scored from 0 (lowest QOL imputed after death) to 7 (best QOL, maximum health). Responses are averaged for composite overall and domain-specific scores, giving equal weight to each question and domain. Subjects' data after revascularization or major amputation will be included in the analysis. However, after death, subjects will be scored as 0. For the effect of treatment on individual domains, pain, symptoms, and activity will be considered the most important of the 5 domains.

Summary statistics will be provided for baseline and change from baseline by visit for each score including total and domain scores. At each visit, only subjects who have a non-missing value at both baseline and the specific visit will be summarized, and two-sided one-sample t-tests for the change-from-baseline will be performed for each visit and LOCF.

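### Does SAP 2.4.3 leave baseline unsettled for Day 0 measurements and for screening retinal exams older than 30 days?

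*SAP*

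**What the plan says.** SAP 2.4.3 sets the reference date as the day of the first injection, Day 0, without a clock time. Its general rule is that "baseline is defined as the last non-missing measurement taken prior to reference start date (excluding unscheduled assessments". The next sentence handles values dated Day 0: "In the case where the last non-missing measurement and the reference start date coincide, that measurement will be considered pre-baseline". That sentence goes on to treat adverse events and medications starting on the same day as post-baseline.

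The protocol treats Day 0 as the baseline visit. The visit-window rows of Tables 3 and 4 carry that label, and a footnote to Table 3 reads "All (non-dosing) follow-up visits should be calculated based on Day 0/Baseline". The Day 0 pre-dosing list in Protocol 5.3.1 includes "QOL Measurements (VascuQol Questionnaire"; the screening list in Protocol 5.1 has no such item. Protocol 9.1, item 8, asks for "Change in VascuQol Questionnaire (QOL) score compared to the baseline at 6, 12 and 18 months", and SAP 2.5.5 adds that "two-sided one-sample t-tests for the change-from-baseline will be performed for each visit and LOCF".

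For the retinal exam, Protocol 4.14 accepts a screening examination done up to 6 months before Day 0, and Protocol 5.1 exempts procedures with their own window from the 30-day screening period. SAP Table 2 runs Screening from Day -30 to before Day 0, and SAP 2.4.3 keeps out-of-window visits in the listings but not in the tables. SAP 2.5.7 plans ETDRS baseline and change from baseline.

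**The concern.** Taken word by word, the two baseline sentences do not fit together. The first requires a value from before Day 0. The second gives a Day 0 value a label that is not *baseline* and is defined nowhere. On a strict reading Day 0 values cannot be baseline. VascuQoL would then have no baseline and its planned change tables would be empty. Rest pain and the pressure indices would be measured from the screening value, which is at least 14 days old and was used to judge eligibility.

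The retinal question is separate. The baseline definition would accept an exam from five months earlier. The Table 2 rule, if applied to the date of the exam, would drop it from a safety table. No sentence says which rule prevails. In both cases the worry is that two programmers could follow the same text and produce different change-from-baseline tables.

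**Working it through.** No power, alpha or sample-size figure bears on this point. The check sets the rules against the assessment schedule, with some day counts.

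**Day 0 values**

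| Measure | Screening (Protocol 5.1) | Day 0 pre-dose (Protocol 5.3.1) | Change from baseline in SAP | Baseline, strict reading | Baseline, evident reading |
|---|---|---|---|---|---|
| VascuQoL | no | yes | yes, 2.5.5 | none | Day 0 |
| VAS rest pain | yes | yes | yes, 2.5.5 | screening | Day 0 |
| Pressures, ABI, TBI | yes | yes | yes, 2.5.5 | screening | Day 0 |
| ETDRS score | yes | no | yes, 2.5.7 | screening exam | screening exam |

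1. The strict reading defeats the SAP's own instruction for VascuQoL. The SAP's schedule of procedures also shows the questionnaire first at Day 0, so only the Day 0 visit is scheduled to supply the baseline that 2.5.5 requires.
2. The same-day sentence starts from the same object as the definition (the most recent recorded value) and contrasts it with events counted as post-baseline. It is a rule for sorting Day 0 records into before and after treatment, and it puts measurements before.
3. The protocol calls Day 0 the baseline.
4. Pre-dose and post-dose values do not get mixed in any planned change table. The scheduled post-dose samples on Day 0 are serum HGF protein and plasmid DNA (Protocol 5.3.3), and SAP 2.5.6 plans no change from baseline for either. The SAP schedule footnotes VascuQoL, VAS and hemodynamics as pre-dose on dosing days.
5. Even on the strict reading the ABI and TBI effect is bounded. Protocol 5.2 says "The assessment will also confirm that hemodynamic measurements have not changed markedly", with a movement of more than 0.1 as the limit. If *d* is the Day 0 value minus the screening value, |*d*| ≤ 0.1 for each stable subject, so the group mean moves by at most 0.1. Appendix B reports that "the index was found to vary by 0.06" but does not say whether that is a standard deviation or a range, so nothing finer is built on it.

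**Retinal exam**

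Inputs: 6-month allowance (Protocol 4.14); 30-day month (Protocol 3), or day 182 for Month 6 (SAP Table 2); Screening window of 30 days (Day -30 to -1).

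- 30-day months: 6 × 30 = 180 permitted days; 180 - 30 = 150 outside the window; 150/180 = 83.3%.
- SAP Month 6: 182 - 30 = 152 outside; 152/182 = 83.5%.

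These are shares of calendar days, not of subjects. Actual exam dates are not in the documents.

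The follow-up exams are safe on either rule. Protocol 4.14 places them 0-14 days before the visit. With visit windows of 7 days either side, the earliest exam for Month 12 is 12 × 30 - 7 - 14 = day 339, and Table 2 opens at 335. For Month 18 it is 18 × 30 - 7 - 14 = day 519, and Table 2 opens at 503. Only the baseline exam is in question.

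For that exam, three features of the text point the same way. SAP 2.4.3 assigns data by the nominal visit on the CRF and tests the date of the visit; the retinal exam is a screening procedure with its own allowance. The section describes its windows as looser than the protocol's, and cutting 180 permitted days to 30 would do the reverse. The baseline definition has no look-back limit.

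**The case for a change.** The best case for a change is that a SAP exists to remove choices before database lock, and this text leaves two. *Pre-baseline* is undefined and collides with the sentence before it. Nothing ranks the baseline definition against the Table 2 window for the retinal exam, and SAP 2.5.7 tabulates only subjects with a baseline value. With 8-10 subjects, each one lost removes 1/10 = 10% to 1/8 = 12.5% of the denominator of a safety table. Two sentences would settle both matters and need no new data.

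The criticism of the wording stands. The SAP is not silent on Day 0, but it is clumsy, and it never mentions the 6-month retinal allowance. The consequences do not stand. Each needs an analyst to choose the reading that contradicts another instruction in the same plan. For VascuQoL the mistake would show at once as an empty table. For ETDRS it would need a visit window to be applied to a procedure date, and SAP 2.4.1 requires listings behind every table, so a dropped exam would be visible.

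**Conclusion.** No change to the plan follows. The wording is loose, but read with the schedules it yields one workable definition: baseline is the most recent scheduled value before the first injection, including pre-dose Day 0 values, and a retinal exam permitted by Protocol 4.14 is the ETDRS baseline. Under that definition no planned summary loses its baseline. The empty VascuQoL tables and the ABI/TBI shift of up to 0.1 arise only under a reading the documents do not support.

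This rests on two assumptions: that analysts read 2.4.3 together with 2.5.5 and the protocol's Day 0 label, and that Table 2 is applied to visit dates as it is written. The number of retinal exams older than 30 days is unknown and may be zero. SAP 2.4.1 treats all testing as descriptive and exploratory, so no inferential claim depends on the point. Writing the definition out would record what analysts will do anyway.

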2.5 Statistical Methods

2.5.1 Study Population

A single study population will be used for all efficacy and safety analyses, that is, the modified Intent-To-Treat population (mITT) population. The population is defined as all subjects who received at least one injection of study treatment.

2.5.2 Disposition, Demographics, Protocol Deviations, and Background Characteristics (Including Medical History)

The number of subjects enrolled (i.e. those who received at least one injection of study treatment) and subjects who completed the study or prematurely discontinued with the primary reason for study discontinuation, completion of the Month 18 clinic visit, and completion of the Month 36 LTFU questionnaire will be summarized.

A table showing number of subjects in the study will be tabulated at Day 0, month 3, month 6, month 9, month 12, month 15, month 18, LTFU (24 month, 30 months, 36 months).

A major protocol deviation is defined as any divergence from the protocol that could have a significant effect on the subject's safety, rights, or welfare and/or on the integrity of the study data, i.e., non-adherence on the part of the subject, the investigator, or the sponsor to protocol-specific inclusion/exclusion criteria, primary objective variable criteria, and/or Good Clinical Practice (GCP) guideline. A minor protocol deviation is defined as either any deviation from the protocol that does not have a significant effect on the participant's safety, rights or welfare, and / or the integrity of the study data or as defined in the protocol or any non-adherence to protocol-specific study procedures or schedules that does not involve inclusion/exclusion criteria, primary objective variable criteria, and/or GCP guidelines and do not impact the study. A listing of subjects with major protocol violations will be provided together with a description of the criteria in the footnotes.

The following demographics, baseline characteristics, and Disease History at baseline will be reported.

- Demographics: age in years, age group (≤ 79 years, > 80 years), sex, race, height, weight, ethnicity
- Baseline characteristics: past tobacco use, current tobacco use, alcohol use, mobility, self-care, anxiety/depression
- Disease History at baseline: Rutherford class, diabetes status with diabetes type, peripheral neuropathy, cardiovascular/lipid history (myocardial infarction, stroke, hypertension, hyperlipidemia), history of index limb (type of peripheral vascular intervention, minor amputation, ulcer status), ischemic rest pain, ankle brachial index (ABI), and toe brachial index (TBI).

2.5.3 Exposure

A listing of subjects' study product administration will be provided. Additionally, a table showing the number of subjects who received only the first course of injections, and the number of subjects who received both the first and subsequent courses will also be provided.

2.5.4 Concomitant Medication

Concomitant medications are medications which started prior to, on, or after the first dose of study medication and taken concomitantly during the treatment period. Concomitant medications will be coded using WHO Drug dictionary version September 2013.

The following concomitant medication listings will be provided: all, medications with indications for MI, stroke, pain, hypertension, and hyperlipidemia by treatment. A listing for subject secondary prevention status at baseline will be provided.

Medications reported as being taken at Screening and Day 0 along with concomitant medications will be summarized by Anatomical Therapeutic Chemical (ATC) classification level 4 description and preferred name.

In addition, the use of statin and anti-platelet agents at screening will be summarized and listed.

